7.5.4 Sensitivity analyses

None planned.

7.6 Pharmacokinetics and pharmacodynamics

None planned. Blood samples were not collected.

7.7 Pharmacogenomics

Acetylation status was determined by bioanalytics in the main study, and categorized into four and two levels for reporting. Descriptive statistics for both will be reported by treatment group.

The two-level categorization of acetylation status will be used to stratify the reporting of safety.

7.8 Exploratory biomarkers

None pre-planned for the clinical study report.

7.9 Safety

The analyses presented in this section will be reported for the Safety population, including all subjects having received any study treatment.

7.9.1 Deaths

The number of deaths will be reported with descriptive statistics by treatment group and relation to study treatment: before, during treatment or within 25 days of stopping, or later.

7.9.2 Adverse events

Adverse events (AEs) will be classified by system organ classes (SOC) and preferred terms (PTs) using the MedDRA dictionary version 23.1.

A treatment-emergent AE (TEAE) is defined as any event arising or worsening after the start of study drug administration until 25 days after the last study medication intake.

A summary of TEAEs and non-TEAEs will be presented, showing total numbers of events and subjects having events:

1. Fatal outcome
2. SAE status
3. Other significant AEs
4. AESI status
5. Causality
6. Severity
7. Actions taken

The number of TEAEs, and number and proportion (%) of subjects having TEAEs by SOC and PT will be given by treatment group. The number of events will also be broken down by:

1. Severity (mild, moderate, severe)
2. Causality (related, not related)
3. Timing with respect to starting treatment (disjoint union of: ≤ 2 weeks, ≤ 4 weeks, ≤ 8 weeks, ≤ 12 weeks, ≤ 24 weeks, ≤ 48 weeks)
4. Dose change groups (see 7.4)

Incidence rates for subjects' first events adjusted for exposure time will also be reported. They are calculated by dividing the number of subjects ever experiencing the event while on treatment by the number of days subjects were exposed to the study treatment.

All serious adverse events (SAEs) and other significant AEs will be evaluated case by case. Narrative descriptions will be included in the study report for all AEs leading to death, other SAEs, AEs leading to study treatment withdrawal, and certain other significant AEs (OSAEs).

Groups of treatment emergent AEs of special interest (AESIs) are defined by Standardized MedDRA Queries (SMQs) where noted, and by in-house search categories (IHSCs) defined as lists of preferred terms, otherwise. Statistics for the following AESIs will be reported:

1. Asthenia or fatigue
2. Decrease in red cell parameters
3. Drug related hepatic disorders - comprehensive search (SMQ)
4. Haemorrhages (SMQ)
5. Headache
6. Hypokalaemia (SMQ)
7. Hypotension
8. Increased heart rate
9. Ischaemic heart disease (SMQ)
10. Neurocognitive disorder
11. Palpitations
12. Suicide/self-injury (SMQ)
13. Supraventricular tachyarrhythmias (SMQ)
14. Ventricular tachyarrhythmias (SMQ)

See Appendix 10.2 for the queries used to create the groups. If an SMQ has both a broad and a narrow definition, the narrow search will be used.

In addition to standard AE reporting, detailed characteristics will be reported for AESIs:

1. SAE status
2. Need for concomitant medications
3. Severity
4. Changes in dosage
5. Outcome
6. Timing with respect to starting treatment
7. Duration of event
8. Safety subgroups (listed in 6.2.14)

Further, for AESIs, 95% confidence intervals (CIs) will be reported for incidence proportions and incidence rates, and risk ratios and incidence rate ratios (with 95% CIs) between the treatment groups will be estimated.

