5.2 Dosing

5.2.1 Selection and timing of doses

All subjects will receive levosimendan in this study. The target maintenance dose of oral levosimendan will be 2 mg/day (see section 5.2.2) taken as 1 mg b.i.d. Levosimendan treatment will be started at 1 mg/day. The subject should be reviewed 2 weeks after initiation of levosimendan at which time the dose should be increased to 2 mg/day, if considered appropriate and the 1 mg/day dose was well tolerated. Since OR-1896 has a very long elimination half-life, it is permitted to use also less frequent dosing than 1 mg once daily (e.g. 1 mg on alternate days) if levosimendan 1 mg/day is not well tolerated. The subject should be re-assessed 2 weeks after each dose change.

Single daily doses should be taken in the morning. It is recommended to take the study treatment about 1 hour before food intake or on an empty stomach. The morning dose of study treatment will be administered at the study centre during the visit days.

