5.2.2 Dose adjustment

The levosimendan dose will be adjusted according to tolerability, including pulse/heart rate. It is recommended to reduce the daily dose of the study treatment (or discontinue the treatment if no further dose reduction is possible) if resting pulse/heart rate is repeatedly > 30 bpm more than the pre-treatment value or the subject has marked symptoms related to tachycardia (see section

6.4.4). It is further advised not to increase the dose at week 2 visit or any later time point if the resting pulse/heart rate change is close to this recommended limit.

After the initial two weeks of treatment with levosimendan 1 mg/day, changes in dose can take place at any time but it should be remembered that the full effect of a dose change may take 2 weeks to develop, at which point the subject should be reassessed before making any further dosing decision.

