7.4 Extent of exposure and treatment compliance

The total number of exposed subjects, the total duration of study treatment exposure (continuous, and categorized both separately and cumulatively at the thresholds of ≤ 4 , ≤ 8 , ≤ 12 , ≤ 24 , and ≤ 48 weeks), and dose levels (in milligrams), averaged over the course of the study as well as at each study visit, will be reported as measures of extent of exposure.

Dose changes will be described by reporting the subject counts in the following categories:

- 1) remained at 1 mg for the entire study (“never increased”)
- 2) uptitrated to 2 mg and remained for the rest of the study (“increased and remained”)
- 3) uptitrated to 2 mg and later downtitrated to 1 mg (“increased, then decreased”)
- 4) downtitrated to 0.5 mg directly (“decreased directly”).

Treatment compliance will be described by reporting the number of dispensed and returned study treatment capsules at each study visit. The number of subjects with treatment interruptions longer than 7 days will be reported with descriptive statistics.

Both extent of exposure and treatment compliance will be tabulated with descriptive statistics.

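### SAP 7.9.2 tabulates TEAE counts in time windows of unequal width, with no denominator and no row after week 48, and in dose-path groups that a TEAE can help form

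*SAP*

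**What the plan says.** SAP 7.9.2 gives the number of TEAEs, and the number and proportion of subjects with them, by SOC and PT and treatment group. It then breaks down event counts only. Item 3 is "Timing with respect to starting treatment (disjoint union of" six windows, with cut-points at 2, 4, 8, 12, 24 and 48 weeks. Item 4 is "Dose change groups (see 7.4". Neither item names a denominator. The exposure-adjusted rate in the same section is a single rate of first events over all exposure days, not a rate per window or per dose group. A TEAE counts "until 25 days after the last study medication intake".

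SAP 7.4 reports exposure duration as a continuous variable and "categorized both separately and cumulatively at the thresholds of" 4, 8, 12, 24 and 48 weeks. It also defines four groups from the whole on-study dose path, including "uptitrated to 2 mg and later downtitrated to 1 mg" and "downtitrated to 0.5 mg directly".

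Protocol 5.2.1 has the dose raised after 2 weeks "if considered appropriate and the 1 mg/day dose was well tolerated". Protocol 5.2.2 recommends a reduction, among other reasons, "if resting pulse/heart rate is repeatedly > 30 bpm more than the pre-treatment value", and lets the dose change at any time after the first two weeks. Protocol 3 sets no 48-week limit on treatment.

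**The concern.** Long-term safety is the primary objective (SAP 3.1), and descriptive AE tables are how this study addresses it. A reader of a table by time since start wants to know whether events become more or less frequent. Raw counts in windows that widen from 2 to 24 weeks mix the event rate with window width and with the number of subjects still followed. The latest period, which matters most for long-term safety, has no row.

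The dose-path table has a different problem. Membership is settled by what happens after treatment starts, and tolerability drives it. An event that blocks the increase or prompts a reduction places the subject in a group, and is then counted there. Someone reading across the groups could take the counts as tolerability at a given dose. No caution stands beside this breakdown.

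**Working it through.** The plan states no event number, rate or power for these tables, so there is no figure to reproduce.

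**Window widths (SAP 7.9.2).** Differencing 0, 2, 4, 8, 12, 24, 48 gives 2, 2, 4, 4, 12 and 24 weeks. At a flat rate with everyone followed for 48 weeks, the share of week 0-48 events is width/48: 4.2, 4.2, 8.3, 8.3, 25 and 50%. For scale, take the 227 subjects of SAP 7.1 and an assumed 0.5 events per subject-year. Then 227 × 0.5 × width/52.18 gives 4.4, 4.4, 8.7, 8.7, 26.1 and 52.2 events.

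**Last window against first, flat rate.** The study ended early (SAP 7.11) and follow-up is not given, so several patterns are assumed. The ratio is person-time in weeks 24-48 divided by person-time in weeks 0-2.

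- Exponential discontinuation at rate λ = ln 2/median: (e^(−24λ) − e^(−48λ)) / (1 − e^(−2λ)).
- Follow-up uniform over 4 to F weeks: the proportion still followed at t is (F − t)/(F − 4). For F = 60, weeks 24-48 hold 24 × 24/56 = 10.3 weeks per subject, against 2 in the first window.

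| Assumed follow-up | Count 24-48 : count 0-2 |
|---|---|
| All followed 48 weeks | 24/2 = 12 |
| Median to discontinuation 96, 48, 24 weeks | 9.3, 7.3, 4.5 |
| Uniform 4-101, 4-80, 4-60 weeks | 8.0, 6.9, 5.1 |

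The underlying rate ratio is 1 in every row.

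**After week 48.** The TEAE period runs 25/7 = 3.6 weeks past the last dose, so a last dose after week 48 − 3.6 = 44.4 already carries it past week 48. Maximum exposure is not stated. If nobody's TEAE period passes week 48, nothing is missing. Under uniform follow-up to F weeks, the share of person-time after week 48 is (F − 48)²/(F² − 16): 4.0, 16.0 and 27.6% for F = 60, 80 and 101. The 101 is the number of weeks from the protocol date (7 January 2019) to the SAP date (16 December 2020), a loose upper bound. All three shares are assumptions.

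**Denominators available.** Five of the six cut-points are also exposure thresholds in SAP 7.4, so rough numbers at risk can be derived. The 2-week cut and an explicit > 48-week class are missing there.

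**Dose-path groups: mechanism only.** Assume the same event rate at every dose, a mean of 2 events over 48 weeks (r = 2/48), and that each event blocks the increase or triggers a reduction with probability q = 0.1.

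- Raised and kept at 2 mg: e^(−48rq) = 81.9% of subjects, with 48r(1 − q) = 1.80 events each.
- Raised, then lowered: e^(−2rq) − e^(−48rq) = 17.3%, with 1.80 + 46rq/(1 − e^(−46rq)) = 2.90 events each.

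Per 100 subjects the counts are 81.9 × 1.80 = 147 and 17.3 × 2.90 = 50. The count ratio, lowered to kept, is 0.34, while the ratio per subject is 1.61, with no dose effect. At q = 0.3 the counts are 54.9 × 1.40 = 77 and 42.6 × 2.71 = 115, and the count ratio becomes 1.5. The contrast between groups is driven by q, and no passage gives q.

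**Paths not clearly assigned.** Protocol 5.2.2 allows later changes in dose, but the four SAP 7.4 groups do not clearly place a re-increase after a reduction, or a move from 2 mg to 0.5 mg.

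**The case against.** The strongest reply is that these are labelled descriptive tables. The SAP tests no hypothesis (section 4), has narrowed its reporting on purpose (7.11) and claims no dose dependence. The window limits are visible in the row labels. Both prior-treatment arms share the same windows, so width alone does not distort a comparison between arms within a row. Actions taken, and changes in dosage for AESIs, already link events to dose. All of this stands, and it is why the point is minor.

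Four stronger readings are tempting and are not supported:

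- *Later rows must show more events.* That follows only if the rate is roughly flat. Protocol 1.2.2 starts at the lower dose to reduce headache and heart-rate increase, so drug-related events may cluster early.
- *The 12-fold ratio is the expected size.* It needs 48 weeks of follow-up for everyone, in a study that stopped early.
- *Late events are lost.* No passage shows a TEAE after week 48. Any such event stays in the SOC/PT totals and could be recovered by subtraction. Deaths, other SAEs and withdrawals due to AEs also receive narratives.
- *The dose-path table is known to mislead in a given direction.* The direction of the count comparison depends on how often an AE changes the dose, which the documents do not state.

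**Conclusion.** The point holds in limited form. Item 3 cannot show whether risk changes over time. At a flat rate the last window would hold roughly 5 to 12 times as many events as the first (4.5 at the shortest follow-up assumed), purely from width and follow-up. The number of events without a row is unknown and may be zero. Item 4 cannot be read as dose dependence, because tolerability decides both dose and group. The worked dose-path figures show the mechanism and are not an estimate of its size.

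Severity is minor. The effect is confined to these two breakdowns and, if it uses the same windows, the AESI timing item in SAP 7.9.2. SOC/PT totals and the overall exposure-adjusted rates are unaffected. Confidence is high on what the SAP specifies; the magnitudes rest on assumed follow-up.

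**What to change.** **Item 3.** Add a > 48-week window. Give subjects at risk, person-time and event rate for each window, with person-time covering the same days in which TEAEs are counted. Add a 2-week cut and an explicit > 48-week class to the SAP 7.4 exposure categories. State that AESI timing uses the same windows.

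**Item 4.** Report the number of subjects and person-time per dose-path group. Footnote that AEs helped form the groups and that the counts do not show dose dependence. Denominators alone do not cure this, as the per-subject ratio above shows, so the footnote is needed. Add an 'other path' category for dose paths not clearly assigned.

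A table by dose at onset, with person-days at that dose, is optional. It is itself biased, because subjects who tolerate the drug are selected into the higher dose, and it would be sparse at some doses.

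The cost is SAP wording and a little programming from exposure and dose records already needed for SAP 7.4, with some sparse cells. The smallest useful version is one extra row and one footnote.

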1.3.2 Potential risks associated with levosimendan

Safety data with oral levosimendan are primarily based on treatment of patients with heart failure and extensive experience with the i.v. preparation, although 66 patients with ALS received levosimendan in the LEVALS study. Available data indicate that levosimendan or its active metabolites do not typically cause clinically significant direct CNS effects. Headache (due to vasodilatation), increased heart rate and palpitations have been the most commonly reported adverse drug reactions in healthy subjects and/or ALS patients treated with levosimendan. Myocardial and arterial changes such as hypertrophy, myocarditis and vasculitis have been observed in toxicity studies in animal species, dog being the most sensitive species with first signs of toxicity appearing at 2-5 fold clinical exposure. The clinical relevance of these findings is not known. Based on the safety data originating from the completed clinical studies with oral levosimendan in chronic heart failure (CHF) (administered 1-2 mg daily for longer than 180 days), safety signals of increased heart rate and palpitations have been detected and are considered as potential risks for oral levosimendan use. No other safety concerns related to cardiac function have been identified from these data. Arrhythmias are known AEs for i.v. levosimendan in patients with severe CHF. However, there is no such evidence for oral levosimendan in healthy subjects. In addition, in the LEVALS, phase IIa study conducted in ALS patients, no differences in supraventricular or ventricular tachyarrhythmias were seen between placebo and levosimendan treatments. There were no differences either in the numbers of severe AEs or serious adverse events (SAEs) between the treatments. However, special attention should be paid to symptoms potentially connected with cardiac arrhythmias, such as palpitations, dizziness and loss of consciousness. In laboratory parameters, slight decreases in red cell parameters and serum potassium have been observed in some studies.

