7.1 Disposition of subjects

329 subjects completed the REFALS study. Of those, 28 were ineligible to continue to the extension study, and 54 otherwise eligible subjects did not wish to continue. Of the remaining 247 subjects who wished to continue, 20 were delayed due to COVID-19 related restrictions, and did not start the study before the recruitment was closed. In total, 227 subjects were screened and started the extension.

The number of subjects will be tabulated by treatment group for the following populations:

- Screened population
- Safety population
- Discontinued study

Separate tables by treatment group will also be provided for each country, and each study centre.

The disposition and number of subjects, along with reasons for screening failure and study discontinuations, will be listed and tabulated by treatment group.

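### The adverse event rate labelled as a first-event rate keeps exposure days after the first event in its denominator, so it reads low for common events

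*SAP*

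**What the plan says.** SAP 7.9.2 introduces the measure with "Incidence rates for subjects' first events adjusted for exposure time will also be reported". The next sentence gives the calculation: "They are calculated by dividing the number of subjects ever experiencing the event while on treatment by the number of days subjects were exposed" to study treatment. Neither the SAP nor the protocol defines a separate time at risk or ends a subject's time at the first event.

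Later in the same section, incidence rates for adverse events of special interest (AESIs) receive 95% confidence intervals, and "risk ratios and incidence rate ratios (with 95% CIs) between the treatment groups will be estimated". The groups are the arms assigned in REFALS (SAP 7).

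Two protocol sections bear on how much this matters. Protocol 1.3.2 states: "Headache (due to vasodilatation), increased heart rate and palpitations have been the most commonly reported adverse drug reactions". All three are AESI groups in SAP 7.9.2. Protocol 5.2.2 addresses a marked rise in heart rate or symptoms of tachycardia: "It is recommended to reduce the daily dose of the study treatment", with discontinuation if the dose cannot be reduced further. The plan therefore expects some subjects to stay on drug after a tolerability event.

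**The concern.** A rate of first events needs a denominator of time during which a first event is still possible. The numerator here fits that, since each subject is counted once. The denominator does not: a subject with headache in week 2 who stays on drug to week 48 contributes 46 further weeks in which another first headache cannot be counted. A programmer who follows the SAP sentence will sum all exposure days.

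The shortfall grows with the share of subjects affected, so it falls mainly on the reactions the protocol itself calls most common. The rates also feed the AESI comparison between prior-levosimendan and prior-placebo subjects, in a study whose primary objective is long-term safety.

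**Working it through.** The documents report no adverse event rate, event proportion or exposure total, so there is no planned figure to reproduce. The check compares the two definitions under stated assumptions.

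**Inputs from the documents**
- SAP 7.1: "In total, 227 subjects were screened and started the extension".
- SAP 6.2.1: 2:1 randomisation in REFALS. The split in the extension is not given. If 2:1 persisted, 227 divides into about 151 and 76.
- SAP 7.4: exposure categories run up to 48 weeks (336 days), used only to choose a follow-up range.

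**Assumed:** proportion affected p, onset pattern, and affected subjects staying on drug.

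**Definitions**
- As written: affected subjects ÷ sum of exposure days.
- At risk: affected subjects ÷ sum of min(days to first event, exposure days).

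Over the same window, each subject's at-risk days are no more than the exposure days, so the as-written rate cannot be the higher one.

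**Step 1. Ratio of as-written to at-risk rate**
- *A, constant hazard, common follow-up T.* At-risk rate = −ln(1−p)/T; as written = p/T; ratio = p/(−ln(1−p)). At p = 0.30: 0.30/0.3567 = 0.841.
- *B, constant hazard, follow-up uniform on 4 to 48 weeks* (28 to 336 days, mean 182). Solve for the hazard h that gives overall proportion p; ratio = (p/182)/h. At p = 0.30 this is 0.804, and a simulation of 2,000,000 subjects also gives 0.804.
- *C, early onset, mean week 4 of 48.* At-risk weeks per subject = 4p + 48(1−p), so ratio = 1 − p × 44/48. At p = 0.30: 0.725.

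Shortfall of the as-written rate:

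| Affected | A | B | C |
|---|---|---|---|
| 2% | 1.0% | 1.2% | 1.8% |
| 10% | 5.1% | 6.3% | 9.2% |
| 30% | 15.9% | 19.6% | 27.5% |
| 40% | 21.7% | 26.8% | 36.7% |

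If drug stops at the event, the two rates coincide (ratio 1.00).

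**Step 2. On the rate scale.** Case A, T = 336 days, p = 0.30:
- as written: 0.30/336 × 36,525 = 32.6 per 100 patient-years;
- at risk: 0.3567/336 × 36,525 = 38.8 per 100 patient-years.

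**Step 3. AESI rate ratio.** With equal follow-up the as-written ratio is (p1/T)/(p2/T) = p1/p2. That is the risk ratio, which SAP 7.9.2 already asks for. The at-risk ratio under a constant hazard is ln(1−p1)/ln(1−p2). Intervals use ratio × exp(±1.96 × √(1/d1 + 1/d2)), with expected events d1 and d2.

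| Affected (151 vs 76 subjects) | Expected events | As written (95% CI) | At risk (95% CI) | Shift on log scale |
|---|---|---|---|---|
| 40% vs 20% | 60.4 vs 15.2 | 2.00 (1.14–3.51) | 2.29 (1.30–4.02) | 0.47 SE |
| 10% vs 5% | 15.1 vs 3.8 | 2.00 (0.65–6.16) | 2.05 (0.67–6.33) | 0.05 SE |

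In both rows the at-risk ratio lies inside the as-written interval.

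**The case against.** The strongest reply is that this is a disclosed choice of measure. On that reading, the words about first events describe the numerator, the words about exposure adjustment describe the denominator, and the formula follows at once. Subjects over total exposure is a usable descriptive statistic, and a single at-risk rate is itself a poor summary when onset is early and the hazard is far from constant. This is why relabelling is an acceptable remedy. It does not remove the mismatch: a reader of a table headed as first-event incidence rates will take the denominator to be time at risk.

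The second reply is that the size is all assumption, and the larger figures need unlikely conditions. SAP 7.11 says the extension ended early, so 48 weeks for everyone is not supported. Prior-levosimendan subjects had to complete 48 weeks of REFALS treatment to enter, which makes high rates of new headache or tachycardia in the larger arm less plausible. Both points are fair. Putting the higher proportion in the prior-placebo arm (40% of 76 = 30.4 events, 20% of 151 = 30.2) gives an as-written ratio of 2.00 (1.21–3.31). The at-risk ratio of 2.29 is still inside, a shift of about 0.53 SE, so the conclusion is the same.

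Third, nothing is decided on these rates. SAP 4 specifies no hypotheses, SAP 7.11 narrows reporting to descriptive statistics, and event timing is tabulated for all treatment-emergent events, which gives a partial check. This holds and limits the severity.

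**Conclusion.** The concern holds, as a minor point. As written, the formula does not give the first-event rate its label promises; the result is at or below that rate, provided both are taken over the same window. The direction follows from the definitions. The size depends on assumed event proportions, onset and continued dosing. Under a constant hazard with equal follow-up the shortfall is about 1% to 5% for events in 2% to 10% of subjects and about 16% to 22% at 30% to 40%. It is larger with staggered follow-up or early onset, and nil if affected subjects stop drug at the event. With similar exposure and stopping in the two groups, AESI rate ratios generally move towards 1, within sampling error at this study's size. Rare AESIs are barely affected.

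**What to change.** For each event, count a subject's person-time from the first dose in the extension to the first occurrence, or to the end of the on-treatment window if there is none. Use that person-time for the incidence rates, the AESI rate ratios and their confidence intervals. The revised sentence should name the window and apply it to numerator and denominator alike, because treatment-emergent events are counted "until 25 days after the last study medication intake" whereas this rate refers to events on treatment. That last item is a clarification only.

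If total exposure days are kept, rename the measure exposure-adjusted subject incidence and drop the reference to first events.

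The cost is one or two SAP sentences and a small programming change, using event and dosing dates already collected. Relabelling alone needs no programming. If person-time is changed and the window is not, reported rates for common events will be somewhat higher.
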